1.1 Background

1.1.1 Basic introduction

Acute respiratory distress syndrome(ARDS) is common syndrome in ICU which is characteristic by diffuse endothelial cell and epithelial damage,inflammatory edema,heterogeneous lung injury and refractory hypoxemia.Mechanical ventilation(MV) is the major treatment for ARDS.Lung protective MV including low tidal volume (LTV),appropriate positive end expiratory pressure(PEEP) and prone position ventilation(PPV) has been proved to improve outcome effectively. Despite these measures, the mortality of ARDS is still high, up to 30-50%.

Airway pressure release ventilation(APRV) is an kind of inverse ratio ventilation that provides consistently high mean airway pressure (mPaw) which preventing alveolar collapse/hyperventilation and recurrent opening/closure theoretically. Clinical trials have shown it to be effective to improve oxygenation and lung compliance in ARDS patients.Animal studies have also shown that compared with low tidal volume ventilation,APRV could improve oxygenation, reduce lung heterogeneity and alveolar over-expansion, reduce lung inflammation and histopathological damage.However, the ventilatory and blood flow changes on local lung tissues of ARDS patients during APRV have not

been confirmed. Moreover, due to the lung heterogeneity in ARDS patients, the increase of mPaw may lead to local lung over-expanded and collapsed simultaneously, which may result in the increase of pulmonary shunt fraction and dead space ventilation. Therefore, bedside monitoring of physiological effects of APRV in ARDS patients' lung would help to better understand the efficacy of APRV in clinical application.

Electrical impedance tomography (EIT) is a noninvasive, nonradiological, real-time bedside lung imaging technology which can monitor local alveolar over-expansion and collapse. In recent years, EIT has been proposed to assess pulmonary perfusion by injecting saline. Therefore, EIT would be an ideal bedside tool to evaluate the effects of APRV on respiratory physiology. We hypothesized that EIT may help to clarify the effects of APRV on local lung ventilation, pulmonary shunt, dead space ventilation and V/Q ratio.

1.1.2 Preliminary Research Basis

In animal models of ARDS, APRV was found to reduce ventilation-induced lung injury (VILI) and improve alveolar heterogeneity.

RCT studies showed that compared with LTV, APRV improved oxygenation and lung compliance, and reduced duration of mechanical ventilation in ARDS patients significantly.

1.2 Study type

A single-center prospective observational study.

1.3 Study basis

ARDS is an acute, diffuse, inflammatory lung injury that results in increased alveolar capillary permeability and lung weight, and loss of aerated lung tissue. Current guidelines for ARDS include LTV for lung protective ventilation to improve oxygenation, which is recommended to all types of ARDS patients. However, the lung injury of ARDS is "heterogeneous", with alveolar collapse and atelectasis in gravity dependent area and over-expansion non-gravity dependent area. Besides, due to the geometric effects, parenchyma at the boundary between unidirectional and aerated parenchyma may bear greater strain and stress. APRV is an kind of inverse ratio ventilation that provides consistently high mean airway pressure (mPaw) to prevent alveolar collapse/hyperventilation and recurrent opening/closure theoretically. Clinical trials showed that APRV can improve oxygenation and lung compliance effectively, and reduce mechanical ventilation duration. Animal models of ARDS also showed that compared with LTV, APRV can improve oxygenation and reduce pulmonary heterogeneity and alveolar over-expansion, reduce lung inflammation and histopathological damage. However, up to now, the changes of ventilatory and blood flow in local lung tissue of ARDS patients during APRV have not been studied. In

addition, due to the high degree of respiratory heterogeneity in ARDS patients, the increase of mPaw may lead to simultaneous hyperexpansion and collapse of local lung tissues, which may be followed by an increase in pulmonary shunt fraction and dead space ventilation. Bedside monitoring of the physiological effects of APRV on the lungs would help to better understand the efficacy of APRV in clinical practice. EIT is a noninvasive, nonradioactive real-time bedside lung imaging tool for monitoring local alveolar over-expansion and collapse. In addition, EIT can be used to assess the V/Q ratio by injecting saline, contributing to a deeper understanding of the respiratory physiology of APRV on local lung tissues.

1.4 Risk and benefit

1.4.1 Known potential risks

Several animal experiments and clinical studies have demonstrated that APRV can effectively improve oxygenation and reduce MV duration. Compared with conventional MV, APRV is relatively safe. Therefore, there is no potential risk in this study.

1.4.2 Probability of injury

Mechanical ventilation is a routine treatment for patients with respiratory failure in the ICU, and its safety is well established.

1.4.3 Degree of injury

The subjects will suffer very minor injuries and have no fatal

adverse events.

1.4.4 Known potential benefits

MV is a routine treatment for ARDS patients. Compared with LTV, APRV ventilation can effectively improve oxygenation and reduce the duration of MV in ARDS patients. However, since APRV was classified as inverse ratio ventilation and relatively complex, it has not been widely applied in clinical practice. In this research, we will clarify the effect of APRV on pulmonary respiration mechanism in ARDS patients by EIT monitoring, and provide more clinical evidence for the application of APRV in ARDS patients.

1.4.5 Assessment of potential risks/benefits

MV is a routine treatment for ARDS patients. APRV is a classical mode of MV that has been used in the treatment for ARDS patients over 20 years. Animal and clinical studies have shown that it can effectively improve oxygenation, reduce the duration of MV and the length of ICU stay with less complications. However, due to the uncertainty of mechanism, Its application is still limited in clinical practice. We hope to further explore the mechanism of APRV through this study and provide sufficient evidence for its clinical promotion in ARDS patients. The potential risks of APRV are similar to those of other MV modes. It is a life-saving treatment for ARDS patients with minimal risks when conducted in appropriate indications and contraindications.

1.4.6 Discussion

APRV is a classical mode of MV that can effectively improve oxygenation in ARDS patients. Its unique characteristic of inverse ratio ventilation helps to increase the time of alveolar gas exchange and effectively improve oxygenation. In addition, it can increase the mean airway pressure to promote the re-aeration of collapsed alveoli. Because the airway pressure is set according to the platform pressure, there is less possibility of barotrauma during APRV.

At present, the effects of APRV on respiratory physiology are mostly limited to animal experimental models of ARDS, and its effects on respiratory physiology of ARDS patients still uncertain. For instance, whether it can improve the heterogeneity of lung lesions, or promote the re-aeration of collapsed alveoli, or improve V/Q ratio in ARDS patients have not been supported by sufficient clinical evidence. EIT is a noninvasive, nonradioactive real-time bedside lung imaging tool for monitoring local alveolar ventilation. We hypothesized that EIT may help to clarify the effects of APRV on local lung ventilation, pulmonary shunt, dead space ventilation and V/Q ratio. We hope that this study will help clinicians to obtain a deeper understanding of APRV and promote its application in ARDS patients.

2. Objective and outcome

Objective: to clarify the effect of APRV on pulmonary ventilation

distribution and V/Q ratio in ARDS patients.

Primary outcome: Effect of 24h APRV on pulmonary ventilation distribution in ARDS patients.

Secondary outcome: Effects of APRV on lung ventilation distribution and V/Q ratio in ARDS patients at different times.

3. Study design

3.1 overall design

A Single center prospective observational study.

ARDS patients who received APRV were monitored by EIT at the time of before APRV and after APRV at 2h, 6h,12h,24h,48h and 72h. MV parameters, respiratory mechanics, results of arterial blood gas analysis, and hemodynamic status were recorded, and cardiac status was monitored by point-of care ultrasound.

Data collecting

- (1) Demographic data: Sex, age, height, weight.
- (2) Vital signs: Organ function including sequential organ function score (SOFA) score, acute physiology and chronic health evaluation II (APACHE II) score.
- (3) physiological and laboratory test: Blood routine, Serum biochemical examination (total protein, albumin (ALB), total bilirubin (TB), aspartate aminotransferase (AST), alanine transaminase (ALT), gamma-glutamyl transpeptidase (GGT), blood urea nitrogen (BUN), serum creatinine (Scr)),

brain natriuretic peptide (BNP), C-reactive protein (CRP), respiratory mechanics, cardiac and hemodynamic status at the time of before APRV, APRV 24h, ARPV 48h and APRV 72h.

3.2 sample size

Referring to previous literatures, the number of patients is generally required to be 20, and the number of patients should be increased to 30 in consideration of shedding and withdrawal.

4. Study population

4.1 Diagnostic criteria

ARDS is diagnosed according to the 2014 Berlin definition.

4.2 Inclusion criteria

The following three items must be met simultaneously:

- (1) Age: >18 years old and <80 years old
- (2) ARDS was diagnosed as moderate to severe according to the 2014 Berlin definition.
- (3) APRV duration is expected to exceed 72 hours.

4.3 Exclusion criteria

Any of the following exclusion criteria is an exclusion:

- (1) APRV contraindications including pneumothorax, severe COPD, severe asthma, and intracranial hypertension
- (2) Pregnancy and perinatal stage
- (3) Severe cardiac dysfunction (NYHA class III or IV, acute coronary

syndrome or persistent ventricular tachyarrhythmia), chronic cardiopulmonary disease resulting in enlargement of the right heart, cardiogenic shock or cardiac perioperative period

(4) Refractory shock

(5) BMI > 35 kg/m²

5. The items and frequency of clinical and laboratory examinations to be performed

Pulmonary gas distribution, pulmonary shunt, and V/Q ratio were monitored by EIT before APRV and 2h, 6h, 12h, 24h, 48h and 72h after APRV. Blood routine, serum biochemistry test, BNP, CRP and arterial blood gas were recorded before APRV and 24h, 48h and 72h after APRV. cardiac status was monitored by point-of-care ultrasound.

6. Evaluation

6.1 Primary and secondary outcome

Primary outcome: the effect of 24h APRV on pulmonary gas distribution monitored by EIT.

Secondary outcome: the effect of APRV on V/Q and pulmonary shunt at each time point monitored by EIT.

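### The objective and outcomes name an effect of APRV, but a single uncontrolled before/after cohort can show only change during APRV

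*Protocol*

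**What the plan says.** Protocol Section 1.2 gives the study type as "A single-center prospective observational study", and Section 3.1 repeats it. The comparison structure is also in Section 3.1: "ARDS patients who received APRV were monitored by EIT at the time of before APRV and after APRV at 2h, 6h,12h,24h,48h and 72h". No concurrent, historical or crossover comparator is defined anywhere.

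The aims are worded causally:
- Section 2: "Objective: to clarify the effect of APRV on pulmonary ventilation" distribution and V/Q ratio.
- Section 6.1: "Primary outcome: the effect of 24h APRV on pulmonary gas distribution monitored by EIT".
- Section 6.1: "Secondary outcome: the effect of APRV on V/Q and pulmonary shunt at each time point monitored by EIT".

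Section 1.4.5 states the hoped-for use: "We hope to further explore the mechanism of APRV through this study and provide sufficient evidence for its clinical promotion in ARDS patients". Section 1.4.6 ends with a similar hope that the study will encourage wider use of APRV. Section 8 plans a Friedman test across the time points, followed where appropriate by Dunn tests with Bonferroni correction, two-sided at 0.05. No sentence limits the causal reading of the result.

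**The concern.** Patients enter when their ARDS is moderate to severe (Section 4.2), and the primary reading comes 24 hours after the switch, with further readings to 72 hours. The protocol itself describes a condition that can move over that time: "ARDS is an acute, diffuse, inflammatory lung injury that results in increased alveolar capillary permeability and lung weight, and loss of aerated lung tissue". Section 1.1.1 also credits prone positioning with improving outcome. The protocol neither standardises it nor lists it among the recorded data, so other care may change alongside the ventilation mode.

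A change at 24 hours could therefore be reported as an APRV effect when it came partly or wholly from recovery, regression from a poor baseline or other treatment. Worsening disease could equally hide a real effect. Either way, the stated conclusion goes beyond what the design can show.

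**Working it through.** **Structure.** For one patient, the change from before APRV to 24h is

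Y(24h) − Y(before) = A + D + R + C,

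where A is the effect of APRV, D the disease course, R the regression from a poor baseline and C the effect of concurrent care. Every patient switches at time 0, and nobody is observed for 24 hours without APRV. Nothing in the design estimates D + R + C, so A cannot be separated from the sum. The Friedman and Dunn tests address whether the sum is zero. Section 8 also names Fisher's exact test, but no second group is defined for it to compare.

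**The plan's own figure.** The only design figure is the sample size in Section 3.2: 20, raised to 30. No effect size, SD or power accompanies it, so there is nothing to reproduce. The confounding does not depend on it.

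**Illustration of size.** Inputs from the protocol:
- 7 time points (before, 2, 6, 12, 24, 48 and 72h);
- n = 20 or 30;
- Friedman test, then Dunn with Bonferroni, two-sided 0.05.

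Assumed, because the documents give no values: APRV effect zero, normal data, equal correlation between time points, drift rising to 24h and then flat. Drift is in units of the SD of the paired differences. All pairs are taken as tested: 7 × 6 / 2 = 21.

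For Dunn, the standard error of a difference in mean ranks is √[k(k+1)/(6n)] with k = 7:
- n = 20: √(56/120) = 0.68
- n = 30: √(56/180) = 0.56

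The per-pair level is 0.05/21 = 0.0024, so the critical z is about 3.04. The mean-rank gap needed is about 0.683 × 3.04 = 2.08 at n = 20 and 0.558 × 3.04 = 1.70 at n = 30.

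Simulated rejection rates with no APRV effect:

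| Drift by 24h (SD of paired differences) | Friedman, n=20 | Friedman, n=30 | Dunn 24h vs before, n=20 | Dunn 24h vs before, n=30 |
|---|---|---|---|---|
| 0.2 | 13% | 14% | 1% | 2% |
| 0.3 | 22% | 34% | 2% | 5% |
| 0.5 | 61% | 83% | 12% | 28% |
| 0.8 | 97% | 100% | 50% | 77% |

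These carry simulation error of a few percentage points. With no drift, the Friedman test rejects in about 5% (n = 20) and 4% (n = 30), as it should.

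**Sensitivity to the shape of the drift.** Suppose instead that drift continues linearly to 72h at 0.2 between-patient SD per 24h, with correlation 0.6. The SD of a paired difference is then √[2(1 − 0.6)] = 0.89 between-patient SD, so this is 0.2/0.89 = 0.22 on the table's scale at 24h. Friedman rejects in about 75% (n = 20) and 91% (n = 30). The corrected 24h contrast rejects in only about 1% and 2%. The overall test is thus the part most exposed to drift, and it covers all time points rather than 24h alone.

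**The case against.** The strongest reply is that the protocol calls itself observational twice, that its endpoints are physiological, and that an uncontrolled before/after study of physiology is a recognised design. All of this stands. A reader might infer that the study needs a control arm or is invalid without one. The documents do not support that: as a description of change during APRV, the design does its job.

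Second, the promotion phrase in Section 1.4.5 is introduced as a hope and sits in the risk/benefit discussion. It is not a prespecified conclusion or decision rule, and no sentence says that the whole before/after difference will be credited to APRV. This also stands. The causal reading comes from the word *effect* in the objective and outcomes together with the hoped-for use. The observational label does not restrain that wording.

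Third, an unadjusted paired signed-rank test would give a more alarming figure, about 54% at n = 20 and a drift of 0.5 SD of the paired differences. Section 8 does not plan that test. The planned corrected 24h contrast gives about 12%, so the larger figure should not be used for the primary comparison.

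Fourth, a reader might take the change from before APRV to 2h as the clean APRV effect. It is less exposed to disease course, but regression from a poor baseline can already enter the first reading after baseline. The mechanism proposed in Section 1.4.6, re-aeration of collapsed alveoli, may also take longer than 2 hours. Section 2 already lists ventilation distribution at different times as a secondary outcome, and Section 8 compares the steps. The choice of 24h as the primary time point is not an error.

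**Conclusion.** The point holds as a mismatch between the stated conclusion and the design. The confounding of APRV with elapsed time is complete and follows from the structure alone, without any assumed number. The rejection rates are illustrations: they rest on an assumed drift, normal data, equal correlation, the stated drift shapes and correction for 21 pairs. They show that the planned Friedman test can easily be significant with no APRV effect, and that the corrected 24h contrast is affected much less unless the drift is large. Severity is moderate, because the study is openly observational, early readings are scheduled, and neither the data collection nor the tests need to change.

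**What to change.** 1. In Sections 2 and 6.1, replace *effect of (24h) APRV on* with *change from before APRV to 24h during APRV in*. Reword the secondary outcomes in the same way for each other time point, and align the objective in Section 2.
2. In Sections 1.4.5 and 1.4.6, remove the statements that the study will support promotion or wider application of APRV. State that an uncontrolled change cannot be attributed to APRV alone.
3. Report the already scheduled 2h and 6h changes beside the 24h change as context. Do not make the 2h change the sole basis for attribution.

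The cost is wording in four sections and a fuller presentation of data already being collected. No patients, procedures or measurements are added. The downside is a more modest claim.

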6.2 Safety evaluation

APRV is a mode of MV for ARDS patients and has been shown to be safe in animal and clinical studies.

7. Adverse events and severe adverse events

Adverse event reports: Adverse medical events that occur in patients receiving APRV, but are not necessarily causally related to treatment.

Reports of serious adverse events: patients receiving APRV experienced events requiring prolonged hospitalization, disability, incapacity to work, life-threatening events or death.

During a clinical trial, the clinical investigators are obligated to take necessary measures to ensure the safety of the patients and to document them timely. If serious adverse events occur during the clinical trial, the investigators should immediately administer appropriate treatment to the subject, and investigators should report to clinical trial unit Ethics committee, provincial or regional food and drug administration and state food and drug administration and sponsor by telephone or fax within 24 hours. At the same time, a written report shall be submitted to the above institutions within 15 days. The serious adverse event that occurred during study must be completed serious adverse event report form on the CRF.

All serious adverse events should be followed up until resolved and returned to baseline. Medical documentation of serious adverse events that proved to be irresolvable/permanent conversion to other treatment or death should be documented in the original documentation and follow-up form as well as results of laboratory and other tests.

The investigators and other responsible persons should analyze and determine the causal relationship between serious adverse events in the

subjects from a clinical perspective.

8. Statistical analysis and methods

Statistical analysis was performed by Prism 4.01. Due to the parameters are abnormal distributed, the data is showed as median (interquartile range).The data obtained at each step were compared using Friedman ANOVA of repeated measurements and, when appropriate, through Dunn post hoc tests using Bonferroni correction.Qualitative data were compared with Fisher's exact test.All comparisons were two-sided, $P < 0.05$ indicates the existence of significant difference.

9. Medical treatment and protection of subjects

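### The primary outcome names no EIT variable and Section 8 does not single out the 24h-versus-baseline contrast, so both can be settled after the data are seen

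*Protocol*

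**What the plan says.** The protocol states the primary outcome twice. Section 2 has "Effect of 24h APRV on pulmonary ventilation distribution in ARDS patients"; Section 6.1 has "the effect of 24h APRV on pulmonary gas distribution monitored by EIT". The label shifts from ventilation to gas distribution. Neither statement gives a variable, a lung region, a unit or a rule that turns an EIT image into one number per patient.

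Section 5 lists what EIT will measure: "Pulmonary gas distribution, pulmonary shunt, and V/Q ratio were monitored by EIT before APRV", and again at 2, 6, 12, 24, 48 and 72 hours. Distribution is thus separated from shunt and V/Q, but it is not broken down further. The background (Section 1.1.1) describes EIT as a technology "which can monitor local alveolar over-expansion and collapse", and Sections 1.3 and 1.4.6 discuss dependent and non-dependent lung, heterogeneity and re-aeration.

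Section 8 summarises data as medians with interquartile ranges. It compares the time steps by Friedman test and then, where called for, by Dunn tests with Bonferroni correction. On the threshold it says "All comparisons were two-sided" and that P < 0.05 "indicates the existence of significant difference". It does not say which comparison decides the primary outcome, how many comparisons the Bonferroni step covers, or what happens if several distribution readings are analysed. Section 3.2 sets 20 patients, raised to 30 for withdrawal, with no effect size or power.

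**The concern.** Ventilation distribution is a concept that several EIT summaries could represent, and they need not agree. Section 1.1.1 itself expects that higher mean airway pressure may over-distend some lung regions while others collapse. A summary of collapse and a summary of over-distension could then point to opposite conclusions about the same patients. If the summary is picked once results are visible, the primary claim is no longer a test of a prior question.

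The deciding test is open in the same way. The outcome is tied to 24 hours, but the analysis treats seven time points alike. A reader cannot tell whether a significant Friedman test is enough, or whether the 24h-versus-baseline Dunn comparison must itself be significant after correction. These two rules behave very differently at this sample size.

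**Working it through.** **Inputs from the protocol.** Two-sided 0.05 (Section 8); 7 time points (Section 3.1); 20 patients before the withdrawal allowance (Section 3.2). The protocol states no primary false-positive rate or power, so there is no figure of its own to reproduce.

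**Assumptions.** The number of distribution readings, k, is not given; I take 3 to 6. The correlations between readings and the effect size below are also assumed.

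**Size of the Bonferroni family.** Six comparisons with baseline give a threshold of 0.05/6 = 0.0083. All pairs number 7 × 6/2 = 21, giving 0.05/21 = 0.0024.

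**Reading A: any significant Friedman test counts as success.** Simulating one null reading with 20 patients and 7 times gave rejection rates of 4.40%, 4.43% and 4.92% in three runs of 10,000, mean 4.58%. For k independent readings the chance of at least one rejection is 1 − (1 − 0.0458)^k:

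- k = 3: 1 − 0.9542³ = 13.1%
- k = 4: 1 − 0.9542⁴ = 17.1%
- k = 5: 1 − 0.9542⁵ = 20.9%
- k = 6: 1 − 0.9542⁶ = 24.5%

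Direct simulation of several readings agrees and shows the effect of correlation:

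| Correlation between readings | k = 3 | k = 5 |
|---|---|---|
| 0 | 12.8% | 21.7% |
| 0.5 | 12.4% | 19.3% |
| 0.8 | 10.8% | 14.8% |

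The Bonferroni step does not act here, because it corrects between time steps within a reading.

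**Reading B: the Bonferroni-corrected Dunn contrast at 24h decides.** Without requiring a significant Friedman test first, the nominal rate for independent readings is 1 − (1 − 0.05/m)^k, where m is the number of comparisons:

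- m = 6: 2.5% (k = 3), 4.1% (k = 5), 4.9% (k = 6)
- m = 21: 0.7% (k = 3), 1.2% (k = 5), 1.4% (k = 6)

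With the Friedman test as a gate, simulation across correlations 0 to 0.8 gave 1.0% to 1.2% (k = 3) and 1.3% to 1.9% (k = 5) for m = 6, and below 1% for m = 21. The false-positive rate is therefore under 5% throughout.

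**What Reading B costs.** I simulated one variable in 20 patients with within-patient correlation 0.5 and the same shift at every post-APRV time, equal to 0.7 SD of the paired difference. Power to declare 24h different from baseline:

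| Procedure | Power |
|---|---|
| One Wilcoxon signed-rank test at 0.05 | about 82% |
| Friedman, then Dunn with 6 comparisons | about 47% |
| Friedman, then Dunn with 21 comparisons | about 33% |

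**The case against.** The strongest reply is that the plan, read naturally, does not inflate error at all. The primary outcome is the 24-hour effect, so the claim should pass through the corrected Dunn comparison, and the false-positive rate is then well below 5% even with six readings. That stands. A reader might infer that the primary false-positive rate of this trial is 15% to 25%. The documents do not support that as a fact: it needs either uncorrected 24h tests on several readings, which Section 8 does not plan, or the rule that any significant Friedman test suffices, which Section 8 neither states nor excludes.

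It is also fair to say that the protocol never lists several readings as primary. Over-expansion, collapse, dependent lung and heterogeneity appear as background on the disease or on what EIT can show. The number of readings is therefore an assumption here.

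A reader might further infer that the lack of a stated paired estimate raises the false-positive rate. It does not. Friedman is already a within-patient test, and the choice of estimator and interval may sit in an analysis plan that is not shown. The study is also described as observational and aims to clarify physiology, so strict confirmatory language would overstate its claims.

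None of this supplies the missing variable. Identifying the primary variable is the protocol's task, and both outcome statements attempt it and stop at a concept. The correction between time steps does not limit which reading is picked.

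**Conclusion.** The point holds as a defect of definition: the primary EIT variable is unnamed and the deciding 24h contrast is not singled out. That conclusion rests on the text alone and needs no error rate.

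The size is conditional. Under the permissive rule with 3 to 6 independent readings, the chance of at least one false positive is about 13% to 25%, and lower with correlation. Under the strict rule the error is controlled, but power for the primary comparison drops from about 82% to about 47% or 33% under the assumed effect. The protocol does not say which rule applies. This should be corrected, but it does not show that the trial's error rate is uncontrolled as written.

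**What to change.** In Sections 2 and 6.1, use one label and name one EIT variable as primary, for example the share of tidal ventilation reaching the gravity-dependent half of the lung. Define the primary quantity as each patient's 24h value minus the pre-APRV value.

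In Section 8, test that quantity once with a two-sided Wilcoxon signed-rank test at 0.05 and report the Hodges-Lehmann paired difference with a 95% confidence interval. With about 20 patients, the interval is what lets a non-significant result be read. Keep Friedman with Bonferroni-corrected Dunn tests for the other readings and times, and label these secondary.

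The cost is a few sentences and no new data. The sponsor gives up the option of claiming the primary result on a different EIT reading. Keeping the corrected Dunn comparison as the primary test would also be valid, provided the variable, the 24h contrast and the number of comparisons are named, but it would carry the loss of power shown above.
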